3.1.3 Phase 2: Therapist Implementation of EBP (FRIENDS & CATS) & Implementation of Support Strategies (TT vs. TT+)

STS therapists from the participating agencies will screen students who have been referred to the STS program and then refer students, who meet the screening criteria, to the research team. If the child has screened positive on either the parent- or child-form of the SCARED, then he or she is eligible to participate in the study. The research team will conduct further evaluations using rating scales to understand symptoms and impairment across different aspects of child behavior (e.g., depressive symptoms, coping skills, disruptive behavior, etc.). STS therapists will conduct treatment groups (FRIENDS or CATS) in the schools during lunch periods, or a non-academic period during the school day. Therapists will be expected to conduct FRIENDS or CATS groups with fidelity.

The agency supervisors will be expected to conduct supervision with therapists. Supervisors will provide one 50-minute supervision session for each treatment session the therapist conducts (12 for FRIENDS, 8 for CATS). The session is divided into group preparation (i.e., discussing referrals, preparing for upcoming session, engaging in problem solving around implementation barriers), and coaching (i.e., performance feedback). Prior to the first session, project staff uploads video-recorded samples of effective implementation of the main components of the treatments, as recorded during a previous implementation of FRIENDS. Periodically, the supervisor encourages therapists to watch the video clips at their convenience. Also, prior to the session, the supervisor will watch a recording of the previous session and select clips for discussion. During the coaching portion of the session, the supervisor will ask for self-reflection of previous sessions and provide performance feedback. Then, the supervisor will provide the therapists with (a) fidelity data and (b) video clips bookmarked from the previous session showing effective and ineffective implementation of FRIENDS/CATS.

Simultaneously, TT and TT+ will be implemented by the research team to support the agency supervisors in supporting their therapists.

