If substantial time (45-90 days) has lapsed between training and the start of intervention, Supervisors will be offered a booster training session after the original training in the weeks before starting their group. The purpose of the booster session is to review key points from the training (e.g., conducting performance feedback) and to answer questions about any aspect of the supervision process. This subsequent training opportunity for agency

supervisors (on how to be effective supervisors to the implementing therapists) will be conducted remotely, or in person.

Supervisors in TT+ (Group C) will receive 8 consultation sessions in the first year using the online platform. The consultation sessions will center on helping the supervisor conduct supervision, and will include performance feedback, implementation fidelity, problem solve implementation barriers and will answer supervisors' questions about the supervision manual. We will monitor whether supervision with therapists takes place regularly for the expected length of time and whether therapists implement the treatments with fidelity. This information will be obtained from group fidelity scores.

Supervisors will be instructed to supervise therapists based only on what they have learned in the consultation sessions.

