3.2.2 Total Number of Study Sites/Total Number of Subjects Projected

The study will be conducted in a minimum of 36 (potentially up to 41) public K-8 schools within the School District of Philadelphia and in collaboration with community mental health agencies, contracted by CBH, in the City of Philadelphia. However, not every school will participate during every project year. It is anticipated that schools will participate in 2 project years.

We expect there to be a minimum of 36-41 agency supervisors (one per school at all times). However, there is a 17% drop-out rate of supervisors across agencies. Therefore, depending on supervisor turnover, the number of enrolled supervisors will be comparable. If

all therapists participate once per school year, we'd expect to enroll 90 agency therapists (1 therapist per school (n=18), per year of the study (n=5) = 18x5 = 90). However, given that therapists may run a second intervention group, we could end up with fewer therapists than expected. Yearly therapist drop out in the agencies is 25%. Therefore, depending on therapist turnover within the agencies, the number of enrolled therapists will also be comparable.

Each of the participating mental health agencies will make available extra supervisors and therapists to serve as alternates in case a supervisor or therapist drops out of the study or terminates employment with the agency for any reason. Alternate supervisors and therapists will be invited to attend the initial trainings. If a supervisor/therapist moves to another school within the same study arm, s/he will be allowed to remain in the study and will be treated as a returning supervisor. Supervisors/therapists in conditions A and B who move to a school assigned to a different study arm can participate in the project pending PI review. Supervisors/therapist in condition C who move to a new school assigned to condition A or B will not be allowed to continue in the study due to potential condition contamination. They will be counted as drop outs.

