The supervisions/consultation sessions will also be coded for interruptions and session length. Service interruption is defined as the degree to which therapists are fully available for supervision and treatment sessions. We will derive three scores averaged over the total number of sessions: a) Projected length of the session in minutes minus time spent on interruptions (e.g., answering a phone call, talking about unrelated topics); b) Number of interruptions; c) Total number of supervision / consultation and treatment sessions per group.

To measure differences between support strategies (TT vs. TT+), agency supervisors (12) and therapists (60) in all groups, including participants who did not complete a treatment group but were consented and trained to participate, will be interviewed regarding their perception of the appropriateness and acceptability of the support they receive. A study staff member will conduct open-ended, semi-structured interviews about the process, feasibility and acceptability of the type of support they receive. Interviewers will follow a script to ask questions of supervisors and therapists (e.g., "How acceptable is the level of support you received for the implementation of the FRIENDS protocol?"; "Was the supervision you received from your agency's supervisor appropriate for running groups with children?"; "Was the consultation you received from the research team appropriate for preparing you to conduct supervision with STS therapists?") These interviews will be conducted at the end of each academic year, or once the treatment groups have completed. Qualitative methods will be used because there are currently no psychometrically validated measures that address these areas.

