Kappa coefficients will be computed; a minimum of .85 will be required for each code. Retraining will be conducted should rater agreement fall below .85. In order to aid with interpretation of results, IE's will randomly select an additional 35% of the interviews and code them, as a measure of inter-rater-reliability. We will conduct a structured content analysis for perceived acceptability and appropriateness. The unit of analysis is each interview. We will create a case-by-variable matrix from the codes. The matrix will have an interviewee identifier number, type of support (i.e., TT, TT+), school, agency, subject demographic information, and codes. The code cells will contain the number of times the participant emitted words or phrases pertaining to perceived acceptability and appropriateness of the support they received. Once acceptability and appropriateness are defined for each interview, percentages for acceptability (% acceptance) and appropriateness (% appropriate) out of the total number of words will be calculated. Comparison of % acceptance and % appropriate between TT, TT+ will be conducted using the Wilcoxon sum rank test.

Datasets from the REDCap and NVivo databases will be combined using the statistical software SAS. Each session will be considered to be a "case" in the qualitative database and will be assigned a unique identifying number that will link it (anonymously) to the quantitative database and individual session information such as fidelity scores.

To measure the differences of implementation between therapists whose supervisors receive TT vs. TT+, means of content fidelity will be calculated with its 95% Confidence interval. Similar analysis will be done regarding process fidelity.

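### The TT vs TT+ acceptability test ranks supervisors and therapists together with no term for role, so its result cannot be attributed to either and is exposed to role differences that a stratified test removes

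*Combined protocol and SAP*

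**What the plan says.** Section 5.3 plans end-of-year interviews to compare the two support strategies, with "agency supervisors (12) and therapists (60) in all groups". Of its three example questions, one concerns supervision by the agency supervisor (a therapist question), one concerns consultation by the research team (a supervisor question), and one asks generally about the level of support.

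Section 6.1 turns each transcript into a percentage for acceptance and a percentage for appropriateness. It states "The unit of analysis is each interview" and lists the data: "The matrix will have an interviewee identifier number, type of support (i.e., TT, TT+), school, agency, subject demographic information, and codes". The comparison is one sentence: "Comparison of % acceptance and % appropriate between TT, TT+ will be conducted using the Wilcoxon sum rank test". No section plans an acceptability analysis by role or stratified by role.

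On what differs between the arms, section 3.1.3 says "Supervisors in TT+ (Group C) will receive 8 consultation sessions in the first year using the online platform". It also says "TT and TT+ will be implemented by the research team to support the agency supervisors in supporting their therapists". Therapists in every arm are supervised by their own agency (sections 3.1.3 and 4.3).

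**The concern.** The two roles receive different things. A supervisor in TT+ gets extra consultation from the research team; a therapist in TT+ gets agency supervision that the consultation is meant to improve. One rank test over both roles answers neither whether supervisors find the extra support more acceptable nor whether therapists notice a difference.

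Two statistical problems follow. If the roles score at different levels, for instance because they are asked about different things, that spread enters the pooled ranking as noise. If the arms also contain different proportions of supervisors, it enters as bias. Turnover, alternates, role switches and repeat supervisors (sections 3.2.2 and 8.1.1) make an equal mix uncertain.

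Comparing TT with TT+ is a primary objective (section 2.1), and this test stands under the Primary Endpoint heading.

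**Working it through.** **The plan's own figures.** The acceptability test has no stated sample size, effect or power. The nearest figures are for therapist fidelity in section 6.3, two-sided 0.05, 30 vs 30:
- Content fidelity: d = 8/10 = 0.80. The t-test gives 86.1%; the plan says 86%.
- Process fidelity: d = 0.7/0.9 = 0.78. The t-test gives 84.2%; the plan says 84%.

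Both reproduce. They show that the plan expects TT+ to change what therapists do.

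**Inputs.** Section 5.3 gives 12 supervisors and 60 therapists. An even split over two arms is 6+30 per arm. If the counts cover all three conditions, it is 4+20. Section 3.2.2 gives 36 to 41 supervisors and 90 therapists; over three conditions, 36/3 = 12 and 90/3 = 30, so 12+30 per arm. The splits, normal scores with SD 1, independent interviews and two-sided 0.05 are assumptions.

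**Dilution of a supervisor effect.** Let w be the supervisor share and f the therapist effect as a fraction of the supervisor effect. The pooled mean difference is the supervisor effect times w + (1 − w)f, so dilution = 1/[w + (1 − w)f].

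| Counts | w | f = 0 | f = 0.25 | f = 0.5 | f = 1 |
|---|---|---|---|---|---|
| 12 and 60 | 12/72 = 0.167 | 6.0 | 2.7 | 1.7 | 1.0 |
| 36 and 90 | 36/126 = 0.286 | 3.5 | 2.2 | 1.6 | 1.0 |
| 41 and 90 | 41/131 = 0.313 | 3.2 | | | |

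A rank-sum test does not estimate a mean difference, so power is the better measure.

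**Power of the pooled and supervisor-only tests** (simulation, no role offset).

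| Per arm | Supervisor effect (SD) | Therapist effect (SD) | Pooled | Supervisors only |
|---|---|---|---|---|
| 6+30 | 1.5 | 0 | 12% | 58% |
| 6+30 | 2.0 | 0 | 16% | 83% |
| 6+30 | 0.8 | 0.4 | 47% | 21% |
| 6+30 | 0.8 | 0.8 | 90% | 21% |
| 12+30 | 1.5 | 0 | 34% | 92% |
| 4+20 | 1.5 | 0 | 9% | 29% |

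Which test has more power depends on how far the effect reaches therapists.

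**Role-stratified test.** The van Elteren statistic ranks within each role. It sums (W − E[W])/(N + 1) over roles and divides by the square root of the summed Var(W)/(N + 1)². With m and k interviews in the two arms and N = m + k, E[W] = m(N + 1)/2 and Var(W) = mk(N + 1)/12. Effects here are 0.8 SD in supervisors and 0.4 SD in therapists:

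| Per arm | Role offset | Pooled | Stratified |
|---|---|---|---|
| 6+30 | none | 47% | 46% |
| 6+30 | 2 SD | 26% | 46% |
| 12+30 | none | 61% | 61% |
| 12+30 | 2 SD | 27% | 60% |

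**Unequal role mix, no TT+ effect.** With 6+30 in one arm, 12+24 in the other and a 2 SD offset, the pooled test rejects about 10% of the time (11% in a repeat run); the stratified test stays near 5%.

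**Limit of stratification.** With 1.5 SD in supervisors, none in therapists and no offset, the stratified test has 12% power, the same as the pooled test.

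**The case against.** The strongest reply is that TT+ works as a cascade. Consultation is there to improve supervision, therapists are asked about that supervision, and section 6.3 powers the contrast on therapist fidelity. If therapists share the effect, pooling gains power: 90% against 21% for supervisors alone at 0.8 SD in both roles. At 1.5 SD in supervisors and a quarter of that in therapists, the two tests are level (58% and 59%). This stands.

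A reader might infer from the 12 and 60 that a real supervisor effect is diluted about sixfold. The documents do not support that as a finding. It needs a therapist effect of exactly zero, which the plan does not assume, and it uses counts that section 3.2.2 does not match; those counts cap dilution at 3.2 to 3.5. Nor do the documents suggest opposite effects in the two roles, although such effects would cancel.

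It can also be said that pooling is inferred from silence, that the demographic information could carry role, that one example question is generic, and that this is a test of word-count percentages with no decision rule. These are fair and limit the weight of the point. They do not supply a role term, and section 6.1 does name a single role (therapists) for the fidelity comparison.

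**Conclusion.** The concern holds in limited form. As written, the plan gives one TT vs TT+ result over two roles with different support, and that result cannot be assigned to either. The clearest statistical gain is from stratifying. It costs about one percentage point of power when the roles score alike, recovers 20 points (26% to 46%) at 6+30 per arm with a 2 SD offset, and holds the error rate near 5% when role mix differs.

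The size of the offset is an assumption; the documents give no score distribution. Therapists share supervisors, schools and agencies, so true power is probably lower than all the figures shown. Dilution lies between 1 and 6 on the section 5.3 counts, and between 1 and about 3.5 on those in 3.2.2. It is not a reason to prefer a supervisor-only test as the main analysis. The powered implementation outcome, therapist fidelity, is unaffected. This is worth correcting but does not threaten the trial.

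**What to change.** In section 6.1:
- Name role as a column of the case matrix.
- Replace the overall Wilcoxon comparison with a role-stratified (van Elteren) rank test of TT vs TT+.
- Report the comparison separately for supervisors and for therapists. Label the supervisor comparison descriptive, since it may be as small as 6 vs 6, or 4 vs 4 if the 12 cover all three conditions.

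In section 5.3, state which conditions the 12 supervisors and 60 therapists cover, and reconcile them with the 36 to 41 supervisors and 90 therapists in section 3.2.2.

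The cost is a few sentences, one column of information already known, and slightly more analysis. Stratification will not rescue power if only supervisors respond; the separate reports are there to show that pattern.

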6.2 Secondary Endpoints

Costs will be assessed by use of generalized linear models (GLM). Links and families for the GLM will be empirically fit to the data using diagnostic tests including the Modified Parks test, Pregibon-Link test, Hosmer-Lemeshow test, and Pearson's correlation test. Measures of effectiveness will be derived from the "clinical" analysis of the trial data. Standard errors will be derived from a nonparametric bootstrap. Point estimates for the cost-effectiveness ratios will be based on the point estimates for the difference in costs and outcomes. Confidence intervals for the cost-effectiveness ratio as well as an acceptability curve will be derived using the point estimates of the differences, their standard errors, and the correlation between the differences. Acceptability curves will allow agency administrators to judge whether the gains in children's outcomes/fidelity are sufficient to justify any increases in cost.

6.3 Sample Size and Power

Number of students and statistical power. It is anticipated that a total of 284 (142 students per treatment protocol) will complete the proposed study. The published reported effect size of FRIENDS has been estimated to equal 0.56 (cohen's *d*). In testing for equivalence of FRIENDS and CATS, using two one-sided tests with sample sizes of 142 in FRIENDS and 142 in CATS achieves 88% power at a 5% significance level when the true difference between the means is 0 (null hypothesis), the standard deviation of the differences in means is assumed to be 11, and the equivalence limits are -4.20 and 4.20.

Number of therapist and statistical power. To compare TT to TT+ for the implementation of CATS (H2a), with 30 therapists in TT and 30 in TT+ achieve 86% power to detect a

difference of 8% between the null hypothesis that both group means are 80% (content fidelity) and the alternative hypothesis that the mean of group TT is 80% with estimated group standard deviations of 10 and 10 (an estimated effect size=.8) and with a significance level (alpha) of 0.05 using a two-sided two-sample t-test. Similarly, group sample sizes of 30 and 30 achieve 84% power to detect a difference of 0.7 in process fidelity between the null hypothesis that both group means are 4 and the alternative hypothesis that the mean of group TT+ is 4.7 with estimated groups standard deviations of 0.9 and 0.9 (an estimated ES= .78) and with a significance level (alpha) of 0.05 using a two-sided two-sample t-test.

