Therapists and supervisors will be randomly assigned to one of three conditions: a) FRIENDS with Train-the-Trainer implementation strategy (i.e., Masters-level supervisors receive training by experts on conducting supervision); b) CATS with Train-the-Trainer strategy; c) CATS using the Train-the-Trainer Plus strategy (i.e., supervisors receive training and consultation by experts on conducting supervision). Effectiveness will be measured by comparing A to B; Implementation will be measured by comparing B to C. Agency therapists will conduct all treatment groups in the schools.

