Given agency structure and high staff turnover rate, consented therapists and supervisors may switch roles in an additional study year dependent on randomized study arm. Similar to procedure stated above, any therapist or supervisor that switches a role in the study in condition A or B can participate in any other condition. If the participant is in condition C, then they can only participate in condition C regardless of a change in school or agency during the duration of the study.

We expect each of the therapists to run one intervention group each per year and we expect each group to be composed of 4-6 eligible and consenting students. Therapists can run a second group if time permits but is not expected for participation. Therefore, we expect to enroll 360 students in the intervention sessions.

Given that some referred students will not meet inclusion criteria and that some will not consent or not attend group, we expect that we will need to consider 426 referred students to yield 360 participating students (based on a 15% attrition rate).

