8 STUDY ADMINISTRATION

8.1 Treatment Assignment Methods

8.1.1 Randomization

Selection and Randomization of schools, therapists and supervisors to intervention conditions:

At least thirty-six schools (potentially up to 41) from mental health agencies will participate in this study. Computerized randomization lists will be generated with random assignment of schools (and therefore, the schools' therapists and supervisors of the agencies participating in this study) to Condition A (FRIENDS/TT), B (CATS/TT), or C (CATS/TT+) with the goal of exposing all agencies to each of the three conditions over the course of the study.

Schools will be stratified according to their size (greater than 625 students (yes/no)). Therefore, a list of 18 schools (including their therapists) will be randomly assigned to the treatment groups and will participate in year 1 of the study (Randomize 1). Schools listed in Randomize 1 will also be used in year 2 while recruiting new therapists and their supervisors (potentially repeat supervisors). We expect this to add 6 new therapists (and their supervisors), per intervention condition, to the study. Schools spanning elementary and middle school grades will run interventions with middle school grades in year 1 and elementary grades in year 2.

From the remaining 18 schools (not randomized yet), a stratified new randomization list will be generated for year two and to be used again in year four (Randomize 2) of the study. As a result, a group of six new therapists and their supervisors (potentially repeat supervisors) per intervention will be recruited for year 3 and a new group of six therapists and their supervisors will be recruited for year 4. Schools spanning elementary and middle school grades will run interventions with middle school grades in year 3 and elementary grades in year 4.

For the 5th year, from the original list of 36 schools using the same stratified randomization method, a new randomization list of schools (Randomize 3) will be generated to recruit a new group of 18 therapists and their supervisors (6 per treatment group). Therefore, a new group of 18 therapists per year (a total of 90 therapists) will participate in this study. Each therapist will participate only one time in this study. In schools spanning elementary and middle school grades, the study conditions will be evenly distributed across grade levels.

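### Section 6.3 powers the FRIENDS–CATS equivalence test on 142 completers per arm, but the 360 students expected in Section 3.2.2 give about 120 per arm, and power of about 81% rather than 88%

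*Combined protocol and SAP*

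**What the plan says.** Section 6.3 gives the number of students behind the primary effectiveness comparison: "It is anticipated that a total of 284 (142 students per treatment protocol) will complete the proposed study". From 142 in FRIENDS and 142 in CATS it states 88% power for two one-sided equivalence tests at 5%, with true difference 0, SD 11 and limits of ±4.20.

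Section 3.2.2 gives the enrolment projection for the whole study: "Therefore, we expect to enroll 360 students in the intervention sessions". The same section says "we expect each group to be composed of 4-6 eligible and consenting students". It reaches 360 from 426 referred students, allowing 15% for those who prove ineligible, do not consent or do not attend.

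The study has three arms: A is FRIENDS with TT, B is CATS with TT, and C is CATS with TT+. The Abstract states "Effectiveness will be measured by comparing A to B; Implementation will be measured by comparing B to C", and Section 3.1 says the same. Section 8.1.1 recruits six therapists per arm each year and concludes that "a new group of 18 therapists per year (a total of 90 therapists) will participate in this study". Section 6.3 uses the same equal split when it powers the support comparison within CATS: "with 30 therapists in TT and 30 in TT+ achieve 86% power".

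**The concern.** The two sections describe the same students, and their counts do not agree. One arm out of three equal arms cannot supply 142 completers if the whole study enrols 360. Section 6.3 counts completers and Section 3.2.2 counts enrolled students, so the true gap is wider than the raw numbers show. The 15% in Section 3.2.2 is already used up between referral and participation. Sections 4.4, 7.2 and 8.4.2 all provide for students leaving after enrolment, and no allowance is made for that.

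At stake is the stated power of one half of the primary objective. If the enrolment projection is the correct figure, the trial is more likely than stated to end without a conclusion on equivalence even when the two programmes have the same effect. The error does not raise the chance of wrongly declaring equivalence.

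**Working it through.** **Inputs.** From 6.3: 142 per group, two one-sided tests at 5%, SD 11, margin 4.20, true difference 0, stated power 88%. From 3.2.2: 360 enrolled, 426 referred, 15% loss between the two, 4 to 6 students per group. From 8.1.1: 90 therapists, 6 per arm per year over 5 years. The SD of 11 is taken as the SD of individual pre-to-post changes; the plan's 88% reproduces on that reading.

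**Step 1: reproduce the plan's figure.** With n per arm, the normal approximation is

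power = 2Φ(4.20/SE − 1.645) − 1, where SE = 11 × √(2/n).

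For n = 142: SE = 1.305, 4.20/1.305 = 3.217, 3.217 − 1.645 = 1.572, Φ = 0.942, power = 88.4%. The exact calculation, integrating over the estimated variance, gives 88.2%. Both round to the stated 88%.

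**Step 2: students per arm from 3.2.2 and 8.1.1.**

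- Therapists per arm: 6 × 5 = 30, and 3 × 30 = 90.
- Students per group: 360/90 = 4.
- Students per arm: 30 × 4 = 120, which is also simply 360/3.
- Arms A and B together: 240. Shortfall against 284: 284 − 240 = 44.

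**Step 3: power at 120 per arm.** SE = 11 × √(2/120) = 1.420, 4.20/1.420 = 2.958, 2.958 − 1.645 = 1.313, Φ = 0.905, power = 81.1%. The exact figure is 80.8%. A simulation of 200,000 trials gave 88.4% at 142 and 80.7% at 120.

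**Step 4: sensitivity.** The documents give no loss rate after enrolment, so the loss rates below are assumptions.

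| Analysed per arm, A vs B | Source | Exact power |
|---|---|---|
| 150 | 5 analysed per group | 90.2% |
| 142 | Section 6.3 | 88.2% |
| 120 | 360/3, no loss | 80.8% |
| 114 | assumed 5% loss | 78.1% |
| 108 | assumed 10% loss | 75.1% |
| 102 | assumed 15% loss | 71.7% |

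**Step 5: what 142 per arm would require.** 3 × 142 = 426 analysed students, 426 − 360 = 66 more than projected, and 142/30 = 4.73 analysed per group. The number 426 is exactly the referred count in Section 3.2.2. This suggests that a count taken before losses was carried into Section 6.3, but it does not prove it.

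All these figures ignore clustering by school and therapist, as Section 6.3 does.

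**The case against.** The strongest reply is that the 120 is inferred. No section allocates students to arms, and both 360 and 284 are projections. Groups may hold 4 to 6 students, so 30 groups give 120 to 180 per arm and 142 lies inside that range. Optional second groups are also allowed. This stands as far as it goes: 142 is reachable. But reaching it in three equal arms means 426 analysed students, and Section 3.2.2 expects 360. An unequal split does not help either: 142 in each of A and B leaves 360 − 284 = 76 students for the 30 groups of arm C, about 2.5 per group, below the stated minimum of 4.

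A second reply is that CATS in Section 6.3 may mean arms B and C together, since Sections 2.1 and 6.1 contrast FRIENDS with CATS without naming arms. Pooling 120 against 240 would give 92.2%, and 86.6% after an assumed 15% loss. But the Abstract and Section 3.1 define effectiveness as A against B, Section 6.3 states a 142:142 split, and FRIENDS would still have about 120. The wording in 6.3 does need clarifying on this point.

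Third, 80% is a conventional benchmark that the plan does not adopt, and just where power crosses it depends on the method: 118 per arm gives 79.9% exactly and 80.2% by the normal approximation. No weight should rest on that threshold.

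Finally, Section 5.3 refers to 60 therapists, not 90. With 60 single groups, 142 per arm would need 142/20 = 7.1 analysed per group, outside the 4 to 6 range. The 120 per arm is unaffected, because it needs only an equal three-way split of 360.

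**Conclusion.** The concern holds. The student numbers in Sections 3.2.2 and 6.3 cannot both be right, and nothing in the documents reconciles them. If 360 is correct, power for A against B is about 81% rather than 88%, and the chance of missing true equivalence is about 19% rather than 12%. This assumes equal arms, every enrolled student analysed, and no allowance for clustering. Any loss lowers power further, to about 72% at an assumed 15%. That the two sections conflict is certain. The 81% is conditional on the equal split, and the source of the error is open: it could lie in either section.

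**What to change.** Reconcile Sections 3.2.2 and 6.3 and say which figure was in error.

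- **If 360 stands:** in 6.3, replace 284 and 142 with the numbers expected to be analysed in arm A and in arm B, about 120 each before loss. Restate power as about 81% with no loss and before any design effect, and show lower values under stated loss assumptions. This costs wording only, and the stated power becomes less favourable.
- **If 142 per arm stands:** correct the 360 and 426 in 3.2.2. The plan then needs 426 analysed over three arms, with enrolment set above that by an expected loss rate that the sponsor should state. As an illustration, an assumed 15% loss gives 426/0.85, about 502 enrolled. Before any loss, the cost is 22 more students per arm (44 in A and B, 66 over three arms). The stated group size accommodates this if all 90 groups run.

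In either case, state in 6.3 that CATS in the equivalence calculation means arm B, in line with the Abstract and Section 3.1.
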